- j Only for subjects who agreed to participate in the population PK sub-set (US and Japan only). Blood and sputum samples will be collected from 0 to 1 hours before and from 1 to 4 hours after study drug administration ([Section 7.4.1](#)).
- k Only for Japanese subjects from sites in Japan who agreed to participate in the comprehensive PK sub-study. Please refer to [APPENDIX 5](#) for additional details on the comprehensive PK sub-study.
- l Study drug will be dispensed to all subjects up to and including the Month 6 visit. At Month 8, subjects who are non-converters or experienced a relapse or recurrence after achieving culture conversion will exit the study at Month 8/EOT visit ([Section 3.1](#), [Section 4.6](#)). Subjects who remain in the study after Month 8 will receive study drug for 12 months beginning from the first of 3 negative cultures that defines culture conversion .
- m If Study INS-312 has been IRB/EC approved, start the ICF consent process at Month 6, in order to provide sufficient time for the subject to make an informed decision

Protocol Amendment #3 version: 22 February 2016

*This protocol is solely for the purpose of communicating information about the investigational drug between Insmad Incorporated and study personnel. Information is not to be reproduced, abstracted or used for sharing of information for any other purpose, whatsoever, except with the written permission of Insmad Incorporated.*

Confidential

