### 7.2.7 Clinical Laboratory Evaluations

The following clinical chemistry, hematology, and urine parameters comprise the clinical laboratory evaluations:

Clinical chemistry	Sodium, chloride, potassium, bicarbonate (CO 2 ), magnesium, calcium, glucose, phosphate, total bilirubin (with direct and indirect fractionation, if total bilirubin is elevated >2 ULN), alkaline phosphatase, lactate dehydrogenase (LDH), aspartate aminotransferase (AST), alanine aminotransferase (ALT), albumin, total protein, creatinine, urea-nitrogen, uric acid, estimated glomerular filtration rate from the Cockcroft-Gault method, and, at Screening only, human chorionic gonadotropin (hCG) pregnancy test for women of child-bearing potential
Hematology	Hemoglobin, erythrocytes, hematocrit, mean corpuscular hemoglobin (MCH), mean corpuscular volume (MCV), mean corpuscular hemoglobin concentration (MCHC), leukocytes, differential blood count of neutrophils, eosinophils, basophils, monocytes, lymphocytes, and platelets.
Urinalysis	Qualitative analysis of glucose, ketones, nitrites, protein, pH, leukocytes, blood, bilirubin, specific gravity; microscopic examination for cells, casts, and bacteria  Urine pregnancy test for women of child-bearing potential. Performed at the site and results will be entered into the eCRF

Protocol Amendment #3 version: 22 February 2016

*This protocol is solely for the purpose of communicating information about the investigational drug between Insmmed Incorporated and study personnel. Information is not to be reproduced, abstracted or used for sharing of information for any other purpose, whatsoever, except with the written permission of Insmmed Incorporated.*

Other

Biomarkers CRP and IL-6

Assessments made only before the first administration of study drug are not considered safety parameters.

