#### **7.2.7.1 Methodology**

Blood samples will be drawn with a minimum number of needle insertions to determine clinical chemistry and hematology parameters at Screening, and before administering study drug on Day 1, at Months 1, 3, 6, 8, and 12, and at EOT. Lab values that meet exclusionary criteria based on results from the central laboratory may be repeated at the Investigator's discretion and sent to the central laboratory provided that the re-evaluation is completed within the protocol defined Screening period and can only be repeated once. Only those labs that need to be re-evaluated should be performed as an unscheduled visit, not the entire laboratory panel. Details for collecting, handling, storing, and transporting blood samples will be provided in the site laboratory manual.

Urine samples will be collected at the same times as blood is drawn.

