### **8.1 DEFINITION OF AN ADVERSE EVENT**

Any untoward medical occurrence in a subject or clinical investigation subject administered a pharmaceutical product and which does not necessarily have to have a causal relationship with this treatment.

An AE can therefore be any unfavorable and unintended sign (including an abnormal laboratory finding, for example), symptom, or disease temporally associated with the use of a medicinal product, whether or not considered related to the medicinal product.

Examples of AEs include one of the following or a combination of 2 or more of these factors:

Protocol Amendment #3 version: 22 February 2016

*This protocol is solely for the purpose of communicating information about the investigational drug between Insmmed Incorporated and study personnel. Information is not to be reproduced, abstracted or used for sharing of information for any other purpose, whatsoever, except with the written permission of Insmmed Incorporated.*

- A new sign, symptom, illness, or syndrome
- Worsening of a concomitant illness
- An effect of investigational product, including comparator or concomitant medication
- An effect of an invasive procedure required by the protocol
- An accident or injury
- Laboratory abnormality that the Investigator considers clinically relevant

Surgical procedures themselves are not AEs; they are therapeutic measures for conditions that require surgery. The condition for which the surgery is required is an AE, if it occurs or is detected during the study period. Surgical measures planned prior to study enrollment are permitted by the clinical study protocol and the condition(s) leading to these measures are not AEs.

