## 8.3 ADVERSE EVENTS OF SPECIAL INTEREST

Adverse events of special interest (AESI) are those known to be attributed to parenteral amikacin:

Protocol Amendment #3 version: 22 February 2016

*This protocol is solely for the purpose of communicating information about the investigational drug between Insmmed Incorporated and study personnel. Information is not to be reproduced, abstracted or used for sharing of information for any other purpose, whatsoever, except with the written permission of Insmmed Incorporated.*

- nephrotoxicity, including elevation of serum creatinine, albuminuria, presence of red and white cells, casts, azotemia, and oliguria
- ototoxicity affecting the eighth cranial nerve resulting in hearing loss, loss of balance, or both.
- neuromuscular disorders
- allergic alveolitis
- bronchospasm
- hemoptysis

Cough is often associated with the drug products that are nebulized. In order to properly characterize AEs of cough, specific details regarding AE of cough will be reported in separate eCRF pages.

It is expected that patients in this study will experience a large number of pulmonary exacerbation events due to their underlying lung condition(s). Pulmonary exacerbation will be defined based on the Investigators best clinical judgment. Details of the type of exacerbation should be provided. These events should not be reported on the AE eCRF unless they meet the criteria for an SAE. Instead, these events should be reported in the “pulmonary exacerbation not SAE” page of the eCRF.

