## **9.7 SAFETY ANALYSIS**

Safety data will be summarized for the Safety Population.

Adverse events will be coded using the agreed upon version of the Medical Dictionary for Regulatory Activities (MedDRA). For non-converters entering the single arm LAI study (Study INS-312), safety monitoring will continue as defined in that protocol. The number and percent of subjects with treatment emergent AEs by system organ class and preferred term will be presented by treatment arm. The severity of the AEs, the relationship to the investigational

Protocol Amendment #3 version: 22 February 2016

*This protocol is solely for the purpose of communicating information about the investigational drug between Insmmed Incorporated and study personnel. Information is not to be reproduced, abstracted or used for sharing of information for any other purpose, whatsoever, except with the written permission of Insmmed Incorporated.*

product, AEs causing study discontinuation, and all treatment emergent SAEs will be similarly presented. Fatal SAEs will also be presented separately in a similar manner.

Vital signs (temperature, systolic and diastolic blood pressure, pulse, pulse oximetry, and respiratory rate) results will be descriptively summarized by treatment arm.

Clinical laboratory test and pulmonary function results will be descriptively presented. Shifts of laboratory results from Baseline (Day 1) to Month 6 and EOT will be presented by treatment arm.

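### Section 9.7 sets the by-arm laboratory shifts at Month 6 and EOT, so a renal change seen only at another draw and resolved by then shows as no shift

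*Protocol*

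**What the plan says.** Section 9.7 makes two statements about laboratory data. The first is general: "Clinical laboratory test and pulmonary function results will be descriptively presented". The second names time points: "Shifts of laboratory results from Baseline (Day 1) to Month 6 and EOT will be presented by treatment arm". The shifts are the only laboratory display that the section expressly says is by arm.

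Section 7.2.7.1 schedules the blood draws "at Screening, and before administering study drug on Day 1, at Months 1, 3, 6, 8, and 12, and at EOT". The chemistry panel in Section 7.2.7 includes "albumin, total protein, creatinine, urea-nitrogen, uric acid, estimated glomerular filtration rate from the Cockcroft-Gault method", and Section 7.2.7.2 sends it to a central laboratory.

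Section 8.3 lists as an adverse event of special interest "nephrotoxicity, including elevation of serum creatinine, albuminuria, presence of red and white cells, casts, azotemia, and oliguria".

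On follow-up, a footnote to Table 3-1 states that "subjects who are non-converters or experienced a relapse or recurrence after achieving culture conversion will exit the study at Month 8/EOT visit". For those subjects Month 8 is therefore the EOT visit. Converters who continue have their EOT 12 months after the conversion date (Section 6.7), which is the date of the first of the three negative cultures (Section 2.1).

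**The concern.** The protocol collects renal chemistry more often than its named shift displays use it. An aminoglycoside effect on the kidney need not persist to Month 6 or EOT: Sections 5.3 and 5.8.4 allow dosing to be interrupted for safety, after which a value may recover. Subjects may enrol with creatinine up to twice the upper limit of normal (Section 4.2), and Table 5-2 warns of co-medications that may cause or worsen nephrotoxicity.

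A subject whose creatinine rises at Month 1 or 3 and has recovered by the named visits counts as unchanged in the shift tables. The other stated by-arm count that could include this subject is the adverse-event table. Entry there depends in part on judgement, since the Section 8.1 examples include "Laboratory abnormality that the Investigator considers clinically relevant", and the investigator knows the treatment (Section 5.6). Shifts in central-laboratory values do not depend on that judgement. What is at stake is how sensitive this objective by-arm view is to a named renal event.

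**Working it through.** The plan gives no figure to reproduce. The check compares the draws scheduled with the draws that the named shifts use.

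**Inputs.** Post-baseline draws: Months 1, 3, 6, 8, 12 and EOT (Section 7.2.7.1, Table 3-1). Shift visits: Month 6 and EOT (Section 9.7). Month 8 is EOT for non-converters and relapsers (Table 3-1 footnote). Up to about 351 randomised, 2:1 (Section 3.6.1). Planning conversion rates: 20% and 5% (Section 9.1).

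**Coverage of scheduled draws.**

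| Subject | Post-baseline draws | In a named shift | Not in one |
|---|---|---|---|
| Leaves at Month 8 | Months 1, 3, 6, 8/EOT (4) | Months 6, 8/EOT (2 of 4, 50%) | Months 1, 3 |
| Continuing converter | Months 1, 3, 6, 8, 12, EOT (6) | Month 6, EOT (2 of 6, 33%) | Months 1, 3, 8, 12 |

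**Interval without a shift time point.** Unless drug is stopped early, the first shift time point is Month 6. Three consecutive monthly negatives by Month 6 put the conversion date at Month 1 to 4. EOT is then at Month 1 + 12 = 13 to Month 4 + 12 = 16. After Month 6, a continuing converter has 13 − 6 = 7 to 16 − 6 = 10 months before the next shift time point, with draws at Months 8 and 12 in between.

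**Would visit means show it?** This part is an illustration. The 1–5% is an assumption, because the protocol gives no rate of renal abnormality. LAI subjects: 351 × 2/3 = 234. Suppose creatinine doubles at one visit in a fraction f of subjects with similar baselines. The arm mean at that visit rises by f × 100% of baseline.

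- f = 1%: 0.01 × 234 = 2.3 subjects; the mean rises by 1%.
- f = 5%: 0.05 × 234 = 11.7 subjects; the mean rises by 5%.

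A reported maximum would show the largest value but not how many subjects rose.

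**Why the added table should stop at Month 8.** Over the whole treatment period continuing converters have two more draws than others, and so two more chances of an extreme value. Let r be the share of converters who leave for relapse at Month 8. At the planning rates and before drop-out, mean draws per subject are 4 + 2 × 0.20 × (1 − r) on LAI and 4 + 2 × 0.05 × (1 − r) on control.

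- r = 0: 4.4 against 4.1.
- r = 0.5: 4.2 against 4.05.
- r = 1: 4.0 against 4.0.

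Through Month 8 the routine schedule is 4 draws for anyone who stays that long. Equality is not exact. Outside Japan a subject may stop drug early and remain to Month 8 (Section 5.12), and stopping drug also calls for the EOT procedures, including chemistry (Section 6.7). Such a subject can have 4 + 1 = 5 panels.

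**The case against.** The strongest reply is that this is a matter of table content. Section 9.4 leaves details of analyses, tables and listings to the SAP. Section 9.7 does not say that shifts will be shown at these visits only, so a worst-value table can be added without contradicting it. The named visits are also sensible: Month 6 is the primary time point, and EOT captures the end of exposure, including Month 8 for non-converters and the stopping visit for those who discontinue drug early.

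A transient rise also has other routes into the report. Laboratory results are presented descriptively with no visit limit. Qualitative urinalysis can appear there as counts and is not part of this point. The adverse-event definition in Section 8.1 covers abnormal laboratory findings, events are graded by CTCAE where applicable (Section 8.2.1), and Section 9.7 tabulates incidence and severity by arm. An independent committee monitors safety (Section 3.6.5). Systemic exposure is described as low: Appendix 3 puts the median AUC at about 13 times below a published mean for intravenous amikacin.

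Most of this stands, and it limits the size of the point. It does not remove it. Section 9.7 chose its time points, so the choice can be judged, and an SAP that follows it literally would have the same gap. Apart from adverse-event reporting, none of the other routes is stated to give a by-arm count of subjects whose renal value changed and then recovered.

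A reader might go further and infer that renal toxicity will be under-reported, or that the comparison between arms is biased. The protocol supports neither. It gives no rate of missed abnormalities, the shift visits are named alike for both arms, and nothing shows that investigators would withhold reports in one arm.

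**Conclusion.** The point holds as a minor weakness in a stated choice. The named shifts use 2 of 4 scheduled post-baseline draws in subjects leaving at Month 8 and 2 of 6 in continuing converters. A change in creatinine, urea nitrogen or estimated GFR confined to the other draws is tabulated as no shift.

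This assumes that a shift compares the baseline category with the category at the named visit, and that the value is back in its baseline category at both named visits. The number of subjects affected cannot be derived from the protocol; the 1–5% illustration shows only that visit means would respond weakly. Nothing here bears on efficacy, on the type I error rate or on what data are collected.

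**What to change.** Add to Section 9.7: *Shifts from Baseline to the worst post-baseline value through Month 8 will also be presented descriptively by treatment arm.* Apply it at least to serum creatinine, estimated GFR and urea nitrogen, with worst meaning highest for creatinine and urea nitrogen and lowest for estimated GFR. Keep the Month 6 and EOT shifts. If a whole-period worst-value table is wanted as well, keep it descriptive and note the unequal number of draws.

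The cost is one sentence and one more table set, with no new samples or visits. A worst-value table picks up some random fluctuation in both arms. The number of draws may also differ slightly between arms, because unscheduled draws and the extra EOT panel in subjects who stop drug early but stay in the study need not be balanced. Showing the number of draws per subject by arm would let a reader judge this.

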## **10 DATA MANAGEMENT**

### **10.1 SOURCE DOCUMENTS**

Study data will be collected on source documents. The Principal Investigator (PI) is responsible for assuring that collected data are complete and accurate. Source documentation (the point of initial recording of a piece of data) should support data collected on the eCRF. Source documents include all recordings of observations or notations of clinical activities and all reports and records necessary for the evaluation and reconstruction of the clinical study.

### **10.2 DATA COLLECTION AND CASE REPORT FORM MONITORING**

All data obtained for this study will be entered into a local regulation (i.e. 21 CFR Part 11 in the USA) compliant Data Management System provided by Inmed or its designee. These data will be recorded with an Electronic Data Capture (EDC) system using eCRFs. The Investigator will ensure the accuracy and completeness of the data reported to the Sponsor. All data entry, modification or deletion will be recorded automatically in an electronic audit trail.

The Investigator will provide access to his/her original records to permit a representative from the Sponsor to verify the proper transcription of data. Data reported in the eCRFs should be consistent with and substantiated by the subject's medical record and original source documents. The eCRF data will be monitored by the Sponsor or designee. The final, completed eCRF Casebook for each subject must be electronically signed and dated by the PI within the EDC

Protocol Amendment #3 version: 22 February 2016

*This protocol is solely for the purpose of communicating information about the investigational drug between Inmed Incorporated and study personnel. Information is not to be reproduced, abstracted or used for sharing of information for any other purpose, whatsoever, except with the written permission of Inmed Incorporated.*

system to signify that the Investigator has reviewed the eCRF and certifies it to be complete and accurate.

The Sponsor will retain the final eCRF data and audit trail. A copy of all completed eCRFs will be provided to the Investigator.

### **10.3 STUDY RECORDS RETENTION**

Study documents should be retained for a minimum of 2 years after the last approval of a marketing application in an International Conference on Harmonisation (ICH) region and until there are no pending or contemplated marketing applications in an ICH region or at least 2 years have elapsed since the formal discontinuation of clinical development of the investigational product. These documents should be retained for a longer period, however, if required by local regulations. No records will be destroyed without the written consent of Insmmed. It is the responsibility of Insmmed to inform the Investigator when these documents no longer need to be retained.

## **11 ETHICAL CONSIDERATIONS**

A copy of the protocol, informed consent forms, other information to be completed by subjects, such as questionnaires and any proposed advertising or recruitment materials, will be submitted to the regulatory authority(ies) and ECs in accordance with country-specific requirements.

All subsequent amendments to the protocol, informed consent documents, and other study documentation referenced above must be submitted and approved in accordance with country-specific requirements.

Periodic study status reports will be submitted to the ECs in accordance with country-specific regulations. Where applicable, the Investigator will be responsible for obtaining IRB/EC approval of the annual continuing review throughout the duration of the study.

The PIs will notify the local IRBs/ECs of violations from the protocol and SAEs.

Protocol Amendment #3 version: 22 February 2016

*This protocol is solely for the purpose of communicating information about the investigational drug between Insmmed Incorporated and study personnel. Information is not to be reproduced, abstracted or used for sharing of information for any other purpose, whatsoever, except with the written permission of Insmmed Incorporated.*

Subjects will be informed that medical care will not be affected by their agreement or refusal to participate in this study, and that they are free to withdraw from the study at any time without prejudice to the clinician patient relationship.

The study will be conducted according to the principles of the Declaration of Helsinki (Fortaleza, Brazil, October 2013), and the ICH E6 Guideline for Good Clinical Practice (GCP). The Sponsor will ensure that the study complies with all local, federal, or country regulatory requirements as applicable. Throughout the study, the Sponsor and its designee will work with the Investigator(s) to ensure proper study protocol implementation and adherence to regulatory requirements as listed in the study protocol.

### **11.1 GOOD CLINICAL PRACTICE**

This study is to be conducted according to globally accepted standards of good clinical practice (as defined in the ICH E6 Guideline for Good Clinical Practice), in agreement with the Declaration of Helsinki and in keeping with local regulations.

### **11.2 DELEGATION OF INVESTIGATOR DUTIES**

The Investigator should ensure that all persons assisting with the trial are adequately qualified, informed about the protocol, any amendments to the protocol, the study treatments, and their trial-related duties and functions.

The Investigator should maintain a list of sub-Investigators and other appropriately qualified persons to whom he or she has delegated significant trial-related duties.

### **11.3 PATIENT INFORMATION AND INFORMED CONSENT**

Before being enrolled in the clinical study, patients must consent to participate after the nature, scope, and possible consequences of the clinical study have been explained in a form understandable to them.

An informed consent document that includes both information about the study and the consent form will be prepared and given to the patient. This document will contain all the elements required by the ICH E6 Guideline for Good Clinical Practice and any additional elements

Protocol Amendment #3 version: 22 February 2016

*This protocol is solely for the purpose of communicating information about the investigational drug between Insmmed Incorporated and study personnel. Information is not to be reproduced, abstracted or used for sharing of information for any other purpose, whatsoever, except with the written permission of Insmmed Incorporated.*

required by local regulations. The document must be in a language understandable to the patient and must specify who informed the patient. Where required by local law, the person who informs the patient must be a physician.

